1. INTRODUCTION & PURPOSE

This document details the rules proposed and the presentation that will be followed, as closely as possible, when analysing and reporting the main results from the ROMIO study.

The purpose of the plan is to:

1. Ensure that the analysis is appropriate for the aims of the trial, reflects good statistical practice, and that interpretation of a priori and post hoc analyses respectively is appropriate.
2. Explain in detail how the data will be handled and analyzed to enable others to perform the actual analysis in the event of sickness or other absence

Additional exploratory or auxiliary analyses of data not specified in the protocol are permitted but fall outside the scope of this analysis plan (although such analyses would be expected to follow Good Statistical Practice).

The analysis strategy will be made available if required by journal editors or referees when the main papers are submitted for publication. Additional analyses suggested by investigators, reviewers or editors will, if considered appropriate, be performed in accordance with the Analysis Plan, but if reported the source of such a post-hoc analysis will be declared.

Revisions of the statistical analysis plan will include a table of changes subsequent to version 1.0.

2. SYNOPSIS OF STUDY DESIGN AND PROCEDURES

2.1 Trial objectives and aims

The following study synopsis has been written with the sole purpose of informing this statistical analysis plan. For details of the study to inform any other purpose, the current version of the protocol must be consulted.

2.1.1 Primary objective

To compare, in patients with cancer of the oesophagus and oesophago-gastric junction, the clinical and cost-effectiveness of minimally invasive laparoscopically-assisted (LAO) and open (OO) oesophagectomy procedures in terms of recovery, health-related quality of life, cost and survival.

2.1.2 Secondary objectives

To prospectively document the outcomes of totally minimally invasive oesophagectomy (TMIO) in an embedded study, with patients meeting the study eligibility criteria.

2.2 Trial design and configuration

The core of ROMIO is a multi-centre individually 1:1 randomised two-parallel group surgical trial.

Two centres are randomising 1:1:1 between three groups, the third being TMIO. The analysis of data from the TMIO arm will be conducted separately to the analysis of the core two-group trial, with a focus on fidelity, safety, and any signs of “promise” for the fully minimally invasive procedure increasing the rate of recovery of quality of life.

2.4 Eligibility criteria

2.4.1 Inclusion criteria (abridged)

18 years of age or older

Referred for primary oesophagectomy by the MDT or oesophagectomy following re-staging after neoadjuvant treatment

Confirmed MDT evidence of at least adenocarcinoma or at least squamous cell cancer of the oesophagus or oesophago-gastric junction

Fit for pre-operative anaesthesia and surgery, assessed by the MDT

Measurement that the tumour starts more than 5cm below the crico-pharyngeus

Measurement that the tumour involves less than 4cm of the gastric wall

The final pre-treatment tumour stage is between T1N0M0 and T4aN1M0.

2.4.2 Exclusion criteria (abridged)

Patients with high grade dysplasia

Tumour stage is T4b, or evidence of metastatic disease

Type 3 tumours of the oesophago-gastric junction that are scheduled for total gastrectomy

Patients with squamous cell cancer of the oesophagus who the MDT recommends or who individually elect to undergo definitive chemoradiotherapy

Evidence of previous complex thoracotomies or laparotomies that preclude a minimal access approach

Evidence of previous/concomitant malignancy that would interfere with this treatment protocol

Pregnancy

Patients participating in other trials that would interfere with the implementation of this protocol at a particular site.

2.5 Description of interventions

Oesophagectomy consists of a two-field lymphadenectomy: abdomen and thorax. All study patients in the core two-arm trial undergo the same surgery but are randomly allocated to one of two methods of access.

2.5.1 Open oesophagectomy (OO)

The following approaches are permitted: two-phase (right thoracotomy, laparotomy), three-phase (right thoracotomy, laparotomy, cervical incision) or left thoracoabdominal. Within these boundaries, the location and length of incisions are at each surgeon's discretion. Methods to close the incisions are also at the surgeon's discretion.

2.5.2 "Laparoscopically assisted" oesophagectomy (LAO, a.k.a. "hybrid")

As above, except that access to the abdominal cavity will be achieved with several small (~12mm) incisions (as many as needed) and surgery performed laparoscopically. A larger incision to create a feeding jejunostomy is allowed, but should be less than 8cm in length.

2.6 Randomisation procedures

Randomisation will be carried out after eligibility has been confirmed and consent given. Every effort should be made for surgery to be carried out within two weeks of randomisation; adherence to this will be monitored.

Randomisation will be performed by an authorised member of the local research team using a secure internet-based randomisation system ensuring allocation concealment and the avoidance of selection bias.

Allocation of patients to LAO or OO will be at random, will be conducted separately for each centre, and further stratified by whether the patient has undergone neoadjuvant treatment or not. Randomisation within blocks of varying size will prevent large imbalances in the number of patients in each treatment group, whilst maintaining allocation concealment.

2.7 Sample size and justification

The theoretical advantage of LAO compared to OO for patients is improved short-term recovery with the long-term survival benefit of surgery maintained. Consequently, the primary endpoint is the QLQ C30 Physical Function sub-scale measured at three and six-weeks post-surgery and three months post-randomisation.

For simplicity, and to indicate the minimum statistical power that will be achieved for the comparison of recovery, we consider just the six-week assessment of physical function. The planned analysis, based on the three-week, six-week, and three-month assessments of patient-reported physical function (primary outcome), and the baseline assessment as a covariate, is likely to have greater power than indicated here.

We are assuming that having adjusted analyses for centre, there will be no further need to accommodate clustering of outcomes by surgeon. In fact, as a team of surgeons is involved in each case (in decision-making, in-hospital care, and often in theatre), it would be difficult to do in practice.

A recent review of patient reported outcomes has indicated that the minimum clinically important difference on the QLQ-C30 Physical Function Scale is 0.4 standard deviations (1). Allowance for 5% of patients allocated to LAO undergoing OO, and 10% of patients in each group being found during surgery to have more extensive disease, can be achieved by reducing the effect size to be detected to 0.34 standard deviations. In this situation 182 patients in each group (364 patients in total) will allow a true treatment effect (LAO versus OO) of 0.4 standard deviations to be detected with 90% power at the 5% significance level, when up to 15% of patients are not able to follow their allocated procedure.

Further allowing for up to 10% missing outcome data, e.g. due to the patient being too sick, increases the target sample size to $364/0.9 = 406$ patients in total. Hence our sample size target for the definitive ROMIO trial is 203 patients allocated to LAO and 203 patients allocated to OO.

We agreed with the NIHR on the 24th January 2019 to extend recruitment until September 2019 to allow 300 patients to be recruited to the main study. The remaining (approx. 120) patients will come from the external feasibility study cohort. This is treating the feasibility study as an internal pilot, this being possible as it had the same design as the main trial, and it continued to recruit whilst preparations were made for the main trial.

2.8 Blinding

In the first week post-surgery patients will be blinded using large adhesive dressings, positioned similarly on all trial patients regardless of the type of surgery (covering abdominal, thoracic, and cervical incisions). The first dressing should be applied by the surgical team in the operating theatre. The dressing will not be changed unless required; it will then be changed according to local practice. If dressings are changed, the patient will be asked to turn their head away from the wound sites to prevent them from observing the wounds. The nurse will clean the sites of all actual and potential incisions. Dressings will be removed as per local practice at one-week post-surgery. The surgical team will not be blind to allocation.

2.9 Trial committees

ROMIO has a Study Steering Committee (SSC, Independent Chair: [name], Aberdeen University) and a Data Monitoring and Safety Committee (DMSC, Independent Chair: [name], Institute of Cancer Research, London).

The study statistician will provide unblinded analyses, by group, of outcomes and safety measures to closed sessions of the DMSC; no other members of the study management group will see unblinded outcome data (all data collected post-randomisation, unless a case can be made that a measure is unrelated to clinical outcome) prior to the writing of planned publications.

Unblinded analyses by group, for the DMSC, should be restricted to those measures required to monitor patient safety in the trial. Analyses of the clinical outcomes by group, including the primary outcome, should not be conducted routinely unless these are necessary for monitoring patient safety.

Once the study statistician has seen unblinded data, they should not be involved in Study Management Group (SMG) discussions of changes to study conduct.

2.10 Outcome measures

2.10.1 Primary outcome

The primary outcome will be the three assessments of physical function (a subscale of the EORTC QLQ-C30) assessed at three and six-weeks post-surgery and three months after randomisation.

2.10.2 Secondary outcomes

Secondary outcomes will assess the efficacy of the two approaches (morbidity and safety) and establish oncological markers of quality assurance of surgery which are surrogate markers of long-term survival (detailed histopathology and quality assurance of the radicality of surgery). Secondary outcomes will include:

1. All-cause short and long-term complications
2. Impact of complications up to hospital discharge will be categorised using the Clavien-Dindo System(2).
3. Spirometry measures of forced expiratory volume in one second (FEV₁) and forced vital capacity (FVC)
4. Success of blinding during the first six days post-surgery, using the Bang Blinding Index(3).
5. Generic and disease specific HRQL measures EORTC QLQ-C30(4), and QLQ-OES18(5), multidimensional fatigue inventory (MFI-20)(6), EuroQoL EQ-5D-5L(7) from which we will calculate quality adjusted life years (QALYs).
6. Quality assurance of surgery with histopathological and surgical measures
7. Overall and recurrence-free survival to two years
8. Length of hospital stay, defined as length of primary hospital stage plus readmission within 30 days (and length of primary hospital stay plus length of hospital stay if discharged to community hospital)
9. Further measures of NHS resource use and costs.

The assessment points are pre-surgery, post-surgery at three days, six days, three weeks, and six weeks, and post-randomisation at three, six, nine, twelve, eighteen and 24 months.

2.11 Interim analysis

The study team have not planned any interim analysis of the outcomes data.

An unblinded analysis of complications, collected during the feasibility study, was presented to a closed session of the DMC at the committee's request (25th January 2018).

3. GENERAL ANALYSIS CONSIDERATIONS

3.1 Analysis populations

Each of the following will include participants of the feasibility and main trials, according to the availability of data.

The primary effectiveness analysis will include data from the **“full analysis set”**; all randomised participants **in the groups to which they were allocated** (i.e. according to the intention-to-treat principle) who provide at least one of the three post-treatment assessments of physical function contributing to the primary outcome.

The **“safety set”** will include all randomised participants for whom there was an attempt to complete a study procedure (OO or LAO). This does not include patients for whom curative surgery did not proceed (e.g. due to the discovery of more advanced disease). The safety set does include participants who underwent a study procedure which was not that allocated, and participants who needed to convert from LAO to OO due to clinical reasons. This is the analysis population that will be used in the reporting of complications and adverse events. The groups to be compared will be defined by the study procedure **first initiated**, e.g. participants will be retained in the LAO group, even if they subsequently needed to convert to OO.

The **“per protocol set”** will include all randomised participants, **in their allocated groups**, for whom the allocated surgery was completed. Analyses of blinding, and surgical quality will use data from these participants.

Within the above three sets, about 120 feasibility phase patients, allocated to OO or LAO and with the necessary data, will be distinguished from those patients allocated to OO and LAO in the main study. In general, estimates of effectiveness will be stratified by feasibility and main study, and presented with a third pooled estimate using data from the two study phases.

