6.4.4 Surgical complications during hospital stay

Using the safety set, the null hypothesis of true equality in the proportion of patients experiencing one or more episodes of each of the key complications (oesophagoenteric leak, conduit failure, chyle leak, pneumonia, GI bleeding requiring intervention) will be tested using a chi-square test.

For each patient the most severe impact of any complications during their initial hospital stay will be categorised using the Clavien-Dindo system(2), patients in the LAO and OO groups being compared using ordered logistic regression.

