8. FIGURES AND TABLES FOR JOURNAL PUBLICATION OF PRIMARY ANALYSIS

The following are the intended figures and tables for the main journal publications of the ROMIO results. Numbered tables and figures will be presented in the initial paper, those indexed by letters will appear in the subsequent paper.

Table 1. Baseline Characteristics by allocated surgery

	OO (n=)	LAO (n=)
Male; n (%)		
Mean age (SD), n		
Mean BMI (SD), n		
Mean POSSUM physiological score (SD), n		
WHO performance status score, n (%)		
0		
1		
2		
Tumour histologic findings; n (%)		
Adenocarcinoma		
Squamous cell carcinoma		
Adenosquamous		
Other		
Location of tumour in oesophagus; n (%)		
Upper third		
Middle third		
Lower third / Siewert I		
Junctional tumour, Siewert II		
Junctional tumour, Siewert III		
Clinical tumour classification; n (%)		
cT1		
cT2		
cT3		
cT4a		
Clinical node classification; n (%)		
cN0		
cN1		
cN2		
Neoadjuvant treatment; n (%)		
Chemotherapy		
Chemoradiotherapy		
None		

Table 2. Post-surgical recovery of physical function by allocated surgery (primary analysis)

	OO (n=)	LAO (n=)
PRIMARY ANALYSIS – pooled estimate		
Pre-randomisation mean (SD) n		
Three-week post-surgery mean (SD) n		
Six-week post-surgery mean (SD) n		
Three-month post-randomisation mean (SD) n		
Treatment effect (95% confidence interval) p-value		
SENSITIVITY ANALYSES		
Adjusted for time from randomization to surgery		
Treatment effect (95% confidence interval)		
Missing outcome data imputed		
Treatment effect (95% confidence interval)		

Table 3. Complications in those participants undergoing allocated surgery. Counts are of patients, who may have experienced more than one complication of a given type

	OO (n=)	LAO (n=)	p-value
Clavien-Dindo Classification of Complications, n (%)			
Normal recovery			
Grade I/II			
Grade IIIa / Grade IIIb			
Grade IVa / Grade IVb			
Grade V (death of patient)			
Key post-operative complications within 31 days of surgery, n (%)			
Oesophagoenteric leak from anastomosis, staple line, or localised conduit necrosis			
Conduit necrosis/failure			
Chyle leak			
Pneumonia / chest infection			
Delayed gastric emptying			
GI bleeding requiring intervention or transfusion			
Acute abdominal wall dehiscence/hernia			
Acute diaphragmatic hernia			
Key post-operative complications between 31 and 90 days of surgery, n (%)			
Oesophagoenteric leak from anastomosis, staple line, or localised conduit necrosis			
Conduit necrosis/failure			
Chyle leak			

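### The safety set leaves out patients whose curative operation was given up, for example for more advanced disease, so their non-fatal complications and Clavien-Dindo grades enter no comparison; three table captions also contradict the set

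*SAP*

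**What the plan says.** Section 3.1 of the SAP admits to the safety set "all randomised participants for whom there was an attempt to complete a study procedure (OO or LAO"). The next sentence takes some patients out: "This does not include patients for whom curative surgery did not proceed (e.g. due to the discovery of more advanced disease"). Patients who had the other study procedure, and those converted from LAO to OO, stay in. On its use, section 3.1 says: "This is the analysis population that will be used in the reporting of complications and adverse events". On grouping it says: "The groups to be compared will be defined by the study procedure" first begun, so an LAO patient who is converted still counts as LAO.

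Section 6.2 uses this set to tabulate complications. Section 6.4.4 uses it for the tests: "Using the safety set, the null hypothesis of true equality in the proportion of patients experiencing one or more episodes" of each key complication, by chi-square. The Clavien-Dindo comparison by ordered logistic regression is in the same section.

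Section 2.7 allows for "10% of patients in each group being found during surgery to have more extensive disease". Section 2.10.2 lists all-cause short- and long-term complications first among the secondary outcomes. Section 5.5 says what is reported when surgery could not be completed: counts in the CONSORT chart and reasons in the text, but no complications.

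The caption of Table 3 in section 8 reads: "Complications in those participants undergoing allocated surgery". Supplementary Tables 1 and X carry the same restriction.

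**The concern.** Leaving out a patient whose operation never began is normal for a safety population. A patient found during surgery to have more extensive disease is different, because the operation was under way. Section 2.5 says the core trial randomises the method of access, and harm from access can occur whether or not the resection follows. Section 3.1 groups patients by the procedure begun, which is an exposure rule, and then drops some of those exposed because of what was found during the operation.

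Two things are at stake. First, the complication comparison is conditioned on an event after randomisation. If the chance of that event, or the complication risk among those who have it, differs between LAO and OO, the comparison no longer describes everyone who was operated on. Second, the plan gives more than one population for the same tables. A patient who received the non-allocated procedure is inside the set under sections 3.1 and 6.4.4 and outside it under the captions.

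**Working it through.** **Inputs**
- Planned size: 203 per arm, 406 in total (section 2.7).
- Allowance for more extensive disease found during surgery: 10% per group (section 2.7).
- Allowance for LAO patients who undergo OO: 5% (section 2.7).
- Unreduced effect (section 2.7): "minimum clinically important difference on the QLQ-C30 Physical Function Scale is 0.4 standard deviations".
- Complication risks: none given in the SAP, so any value is an assumption.

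**The plan's own figures**
- Reduced effect: 0.4 × (1 − 0.05 − 0.10) = 0.34 SD, as stated.
- Sample size for 0.34 SD, 90% power, two-sided 5%: 182 per group, 364 in total, as stated. Power at 182 per group is 90.0%.
- Missing data: 364 / 0.9 = 404.4, or 405 rounded up, against the stated 406. The gap is immaterial.

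The 10% is therefore built into the design.

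**Patients concerned**
- Per arm: 0.10 × 203 = 20.3, about 20.
- In total: 0.10 × 406 = 40.6, about 41.
- Left per arm: 203 − 20 = 183.

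This assumes that every allocated patient had an operation started and that the allowance is fully used. Section 2.7 gives no figure for operations given up for other reasons.

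**Effect on a risk difference, equal removal**

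Let RD_s be the LAO minus OO risk difference in the safety set and d the same difference among those removed. With 10% removed from each arm:

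RD over all started operations = 0.9 × RD_s + 0.1 × d

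| RD_s (points) | d = −20 | d = 0 | d = +20 |
|---|---|---|---|
| 0 | −2 | 0 | +2 |
| −10 | −11 | −9 | −7 |

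**Effect on a risk difference, unequal removal**

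Suppose instead that 12% of LAO and 8% of OO patients were removed, that the risk among those retained was 30% in both arms, and that the risk x among those removed was the same in both (all assumptions). The true difference is then (0.88 × 0.30 + 0.12x) − (0.92 × 0.30 + 0.08x), while the safety set shows zero.
- x = 0: 0.264 − 0.276 = −1.2 points.
- x = 0.60: 0.336 − 0.324 = +1.2 points.

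**Populations side by side**

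| Patient | Sections 3.1, 6.2, 6.4.4 | Captions of Table 3, Supplementary Tables 1 and X |
|---|---|---|
| Had the other study procedure | In, under the procedure begun | Out |
| More extensive disease found, curative operation given up | Out | Not clear |
| Resection attempted, then abandoned for another reason | Not clear | Not clear |

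The third row is unclear under section 3.1 because the inclusion sentence turns on an attempt to complete the procedure, while the exclusion sentence turns on curative surgery not going ahead and gives advanced disease only as an example.

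**The case against.** The strongest defence is that the set is deliberate and partly sensible. Anastomotic leak and conduit failure, two of the five key complications in section 6.4.4, cannot occur without a resection, so a resected denominator suits them. Grouping by the procedure begun is a recognised choice for safety. Section 2.7 uses the same 10% for both groups, and nothing in the SAP shows that detection, or risk after detection, differs by access. The SAP also does not say at what stage of the operation the disease would be found, or how much of the allocated access would have been made by then.

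All of that stands, and it rules out several stronger readings that a reader might infer:
- *That nothing about these patients is counted.* The full analysis set does not exclude them, and it serves survival with 30- and 90-day estimates, hospital stay, pain and lung function (sections 6.2 and 6.4.5 to 6.4.8). Section 6.6 repeats the pain analysis in the per protocol set because patients with uncompleted surgery are in the main one.
- *That every abandoned operation is dropped.* The inclusion sentence could keep a resection that was attempted and then abandoned for another reason.
- *That 10% is an expected abandonment rate.* It is an allowance for diluting the effect size.
- *That access harm differs most in these patients, or that the bias favours one arm.* No passage supports either.

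The mortality and complication tables may also differ, since a death after an abandoned operation can count in the survival analysis but not as Clavien-Dindo grade V. That follows from using two stated populations and is not in itself an error.

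The defence does not cover Clavien-Dindo grade, pneumonia, bleeding, or the cardiac, thromboembolic and wound events in the tables. None of these needs a resection. It also leaves the caption conflict untouched.

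**Conclusion.** The concern holds for complications and Clavien-Dindo grade. Section 3.1 removes patients from the only set used for these outcomes on the strength of a finding made after randomisation and, for those covered by the section 2.7 allowance, during surgery. No other analysis compares their complications. At the allowance this is about 20 patients per arm. The distortion of a risk difference is probably modest: up to 2 points either way around zero if the difference among those removed is within 20 points. That range is assumed, and the SAP settles neither sign nor size. The primary analysis is unaffected.

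Two drafting faults hold without any assumption. The inclusion and exclusion sentences of section 3.1 leave resections abandoned for other reasons undecided, and the three captions contradict sections 3.1 and 6.4.4.

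**What to change.** 1. In section 3.1, define the safety set as all randomised patients in whom a study operation was started, grouped by the procedure first begun. State what counts as the start, so that the two sentences no longer conflict.
2. Use this set for Clavien-Dindo grade and for general complications such as pneumonia, bleeding, cardiac, thromboembolic and wound events.
3. Keep the present set only as the denominator for complications that need a resection (anastomotic leak, conduit necrosis or failure). Assign the remaining listed items, such as chyle leak, to one denominator in advance.
4. Change the captions of Table 3, Supplementary Table 1 and Supplementary Table X to name the set used, and carry the change into sections 6.2 and 6.4.4.

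The cost is mostly wording. Complication data are needed for patients whose resection was abandoned, and the tables will carry two denominators, which must be labelled.
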